Two recent papers have addressed the issue of finite therapy in patients with HBeAg negative chronic HBV infection (7,8). The original paper by Hadziyiannis and colleagues assessed nucleos(t)ide withdrawal after a minimum of four years' treatment in a group of patients infected with HBV genotype D. These patients were allowed to undergo a virological flare and were followed up for 6 years. Eventually, 30% lost HBsAg. In contrast, Seto assessed the impact of nucleos(t)ide withdrawal in 184 patients infected with HBV genotypes B or C after two years of treatment. Hepatitic flares or resumption of high level viral replication was not permitted so the majority of patients returned to drug treatment. Interim analysis of a similar study presented by Berg et al at EASL 2015 confirmed the findings of Hadziyiannis up to one year after nucleos(t)ide cessation.

High level viral replication is associated with suppression of HBV-specific adaptive immune responses leading to viral persistence (9). Recent data suggest that there is partial restoration of immune responses in patients on long term treatment with antiviral drugs that suppress viral replication (10).

Interferon (standard or pegylated) has been used in the treatment of HBV for 20 years due to its antiviral and immunostimulatory effects. Combining interferon with nucleos(t)ide analogues as initial treatment for HBV infection does not improve therapeutic efficacy (4). However, a number of authorities now believe that sequential therapy (with or without a short break) may amplify immune responses due to the complementary immunological effects of IFN and nucleos(t)ide analogues on innate and adaptive arms respectively and result in increased rates of HBsAg clearance. Based on

NUC-B PROTOCOL Version 2.0 12 th Aug 2016	Sponsor Imperial College
--	-----------------------------

the above, we argue that it is timely to evaluate management options which may result in a cure of HBV, release patients from indefinite drug treatment and increase cost effective care.

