3.2 Design

The main trial for NUC-B will be performed in at least 10 sites in England. It is a randomised, open-label, multicentre trial comparing nucleoside / nucleotide analogue withdrawal against nucleoside/ nucleotide analogue withdrawal followed by a 16 week course of pegylated interferon in HBeAg-negative chronic hepatitis B virus infected patients. Patients will be followed for 3 years after randomisation.

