5.2 Randomisation

Patients will be electronically randomised using the InForm eCRF online custom built database to the two management arms in equal proportions using variable block sizes. Randomisation will be stratified by gender and by HBsAg titre at baseline (< or \ge 2000 IU/mI) as this is the strongest predictor of clinical outcome in interferon based treatment and was found to be a predictor of outcome in the Hadziyannis study.

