8 STATISTICAL ANALYSES

8.1 Sample Size and power considerations

HBsAg loss is the primary endpoint; the trial will compare the rate of HBsAg loss in patients three years after cessation of nucleos(t)ide analogues with the rate of HBsAg loss in patients treated with pegylated interferon after cessation of nucleos(t)ide analogues. Only one published study provides an estimate of the rate of HBsAg loss in patients who stopped treatment after 4 years of nucleos(t)ide analogues which was 10% at 1 year,18% at 2 years and 24% at 3 years. A similar study reported by Berg (EASL 2015) confirmed the 10% HBsAg loss reported at 1 year. In the present study we will recruit some patients who have had treatment with nucleos(t)ide analogues for only 3 years and we will therefore use a conservative assumption for the rate of HBsAg loss in this group at 15% at 2 years and 20% at 3 years.

There is no data on the rate of HBsAg loss in patients who have been treated with nucleos(t)ide analogues and subsequently been treated with pegylated interferon. In a trial of pegylated interferon for naïve HBeAg negative hepatitis infection 42.4% had lost HBsAg at the end of follow up if the level of HBV DNA had been <70 IU/ml at the end of treatment. As this is an exploratory study we have assumed that the rate of HBsAg loss in this group will be 30% at 2 years and 40% at 3 years. This increment would represent the very significant clinical benefit which would justify the use of interferon (with associated side effects) in this group of patients.

A trial with 90% power to detect a difference in HBsAg loss between these groups (40% vs 20%) at the P < 0.05 threshold would require 109 subjects in each arm. Therefore allowing for ~10% withdrawal / dropout in each arm we will aim to recruit 120 subjects to each arm; a total of 240 patients in total. If either arm is discontinued after the pilot, then there will still be at least 80% power in comparison with an alternative trial arm in the post pilot participants.

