8.2 Data Analysis

(i) Primary Endpoint Analysis

This analysis will be performed primarily on an intention to treat (ITT) basis. The ITT population will be all subjects who have been randomized. Secondarily, a per protocol analysis will be performed. The per protocol population will be those confirmed to be eligible who have not resumed nucleos(t)ide analogues for patient/ physician preference and those, in the interferon arm, who have completed at least 8 weeks of interferon therapy. Rates of HBsAg loss will be compared between the two groups using logistic regression adjusting for the stratification factors HBsAg titre and centre. Results will be presented as odds ratios and their 95% confidence intervals.

(ii) Secondary outcomes

Secondary outcomes to be compared between the two groups will include the primary outcome assessed at one year and at two years from baseline. Kaplan-Meier plots will be produced to show the persistence of HBsAg. The plots will be supported by formal secondary analyses using Cox proportional hazards model methods

Achievement of the inactive carrier state (defined above) will be analysed using the same procedures as the primary outcome. A statistical analysis plan will be developed and approved by the Trial Steering committee prior to any regular analysis for reports to the Data Monitoring Committee. This plan will include details of the statistical methods to be used to analyse the outcomes, and describe the methods to undertake sensitivity analyses for handling missing data. The plan will contain conform with the Clinical Trials Unit standard operating procedures

(iii) Predictors of HBsAg Loss

Predictive factors for HBsAg loss will be explored using univariate and multivariate logistic regression analysis. Separate models will be fitted for the following variables: gender, age, duration of antiviral therapy, viral genotype, viral load pre-treatment, HBsAg titre, centre, peak ALT value post withdrawal, peak viral load post withdrawal, hepatic cccDNA, number of infected hepatocytes and ELISPOT counts. Odds ratios and their 95% confidence intervals produced from each of the models will be presented. Following this, a multivariate logistic regression analysis will be performed will include the variables that were statistically significant in the univariate analysis plus a variable for treatment group.

(iv) Safety analysis

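### The single-variable predictor models in section 8.2(iii) omit treatment group, so for markers measured after randomisation the reported odds ratios can be confounded by arm and a real predictor can be screened out

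*Protocol*

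**What the plan says.** Section 8.2(iii) of the protocol sets out two stages.

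- **Stage 1.** A separate logistic model for each of 12 variables: gender, age, duration of antiviral therapy, genotype, pre-treatment viral load, HBsAg titre, centre, peak ALT and peak viral load after withdrawal, cccDNA, number of infected hepatocytes, and ELISPOT counts. Treatment group is not listed. The results are to be reported: "Odds ratios and their 95% confidence intervals produced from each of the models will be presented".
- **Stage 2.** One multivariable model containing "the variables that were statistically significant in the univariate analysis plus a variable for treatment group".

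Treatment group therefore appears only after stage 1 has decided which variables survive. The threshold for significance at stage 1 is not given. The procedure is written into the protocol, so it is not a detail left to the SAP.

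**The concern.** In a pooled single-variable model, a marker that differs by arm picks up part of the arm effect on the outcome. The trial is planned on a large arm effect: section 8.1 assumes 20% HBsAg loss with withdrawal alone and 40% with interferon.

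Peak ALT and peak viral load are recorded after randomisation, and the protocol gives reasons why they might differ by arm:

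- Section 1 says interferon is used "due to its antiviral and immunostimulatory effects".
- The schedules in section 5.3 measure HBV DNA and liver function at 14 post-baseline visits in the interferon arm and 11 in the control arm. A maximum over more samples tends to be higher even with no drug effect.
- Section 6.5 lets patients resume nucleos(t)ide analogues partly on investigator or patient opinion, in an open-label trial. Resumption can cut a peak short.

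Two errors can follow. A marker with no association inside either arm can be presented with an odds ratio away from 1. A real predictor that interferon moves the other way can fail stage 1 and never reach the model that contains treatment. Secondary objective 4 and the prognostic models of section 2.5 bear on the same question.

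**Working it through.** **Inputs from the protocol.** HBsAg loss 20% vs 40% (section 8.1); 109 evaluable per arm (section 8.1); allocation "in equal proportions using variable block sizes" (section 5.2).

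**Assumptions.** Screen at two-sided 0.05. Marker normally distributed with SD 1 within each arm. Shift of d SD between arms, from 0 to 1.0. The protocol gives no figure for d.

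**The plan's own figure.** Section 8.1 says the comparison "at the P < 0.05 threshold would require 109 subjects in each arm". With two-sided alpha, pooled variance and no continuity correction:

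n = [1.960·√(2×0.30×0.70) + 1.282·√(0.40×0.60 + 0.20×0.80)]² / 0.20² = (1.270 + 0.811)² / 0.04 ≈ 108.2, so 109. It reproduces.

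**Size of the confounding, by hand.** With equal arms, the between-arm covariance of marker and outcome is d×(0.40−0.20)/4 = 0.05d, and the pooled marker variance is 1 + d²/4. Dividing the linear slope by 0.30×0.70 = 0.21 gives an approximate log odds ratio.

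Marker with no within-arm association:
- d = 0.25: 0.0125/1.0156/0.21 = 0.059, odds ratio 1.06
- d = 0.5: 0.025/1.0625/0.21 = 0.112, odds ratio 1.12
- d = 1.0: 0.05/1.25/0.21 = 0.190, odds ratio 1.21

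Real predictor, within-arm odds ratio 1.5, shifted against its own direction. The within-arm covariance is about ln(1.5)×(0.16+0.24)/2 = 0.405×0.20 = 0.081, so the numerator becomes 0.081 − 0.05d:
- d = 0.25: 0.0685/1.0156/0.21 = 0.321, odds ratio 1.38
- d = 0.5: 0.056/1.0625/0.21 = 0.251, odds ratio 1.29
- d = 1.0: 0.031/1.25/0.21 = 0.118, odds ratio 1.13

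Simulated mean odds ratios were 1.06, 1.12 and 1.21 for the first set and 1.38, 1.28 and 1.12 for the second, in close agreement.

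**Chance of being called significant.** Simulation with 4,000 trials per setting, 109 per arm, Wald test:

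| Shift (SD) | No within-arm association: as planned | Same, arm included | Real predictor, opposing shift: as planned | Same, arm included |
|---|---|---|---|---|
| 0 | 4.9% | 5.2% | 71% | 73% |
| 0.25 | 5.9% | 4.4% | 56% | 73% |
| 0.5 | 10.6% | 4.3% | 38% | 74% |
| 0.75 | 20.6% | 4.7% | 23% | 74% |
| 1.0 | 29.1% | 4.8% | 13% | 74% |

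The simulation error is about half a point at 10.6% (√(0.106×0.894/4000) = 0.005). Separate runs at 108 and 120 per arm gave about 12% and 14% at 0.5 SD.

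**Where the harm shrinks.**
- Both stages together: a marker with no within-arm association that passes stage 1 must also be significant beside treatment group. It does both in under 5% of trials at every shift tried (about 2–3% at 0.25 to 1.0 SD).
- Smaller arm effect: at a 0.5 SD shift, false passage of stage 1 is 6.7% if loss is 20% vs 30%, and 5.1% if it is 20% in both arms.
- Same-direction shift: a real predictor that interferon moves its own way passes stage 1 in 83%, 91% and 96% of trials at 0.25, 0.5 and 1.0 SD, and both stages in 73–74%. No detection is lost, although the univariate odds ratio is overstated.

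**The case against.** **Few variables are affected.** A reader might infer that interferon shifts several of the 12 candidates. The protocol does not say so. Gender, age, therapy duration, pre-treatment viral load, centre and the stratifying HBsAg titre precede treatment. The biopsy measures are taken between screening and baseline, and genotype is sampled at week 4, before interferon starts. Sections 1.2.1 and 1.4 say interferon amplifies NK cell but not T cell responses; ELISPOT counts T cells, and NK measures are not on the list. This stands: the point concerns two variables, and ELISPOT only if post-baseline values are used.

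**The final model already contains treatment group.** A reader might infer that spurious markers will end up as final predictors. They mostly will not, as the two-stage rates show. What remains is a misleading odds ratio in the univariate table.

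**Loss of a real predictor needs an opposing shift.** The protocol gives no direction for either peak variable. Both arms share an untreated first four weeks and interferon ends at week 20, so a peak may fall outside treatment. This also stands, and makes the 56%, 38% and 13% conditional figures. The loss arises because stage 1 significance alone governs entry; the final model cannot restore what it never receives.

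**Prediction does not need an unconfounded odds ratio.** That is true in general. Here, however, the protocol's own final model conditions on treatment group, so screening on a quantity that ignores it is inconsistent with that target.

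**Conclusion.** The point holds in limited form. Stage 1 omits treatment group, presents the resulting odds ratios and alone decides entry to the model that contains it. For peak ALT and peak viral load, and for ELISPOT if measured after baseline, this can distort the reported univariate odds ratio and can discard a real predictor. The second is the more serious, because it cannot be repaired later.

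The size rests on an assumed marker shift and on the planned arm effect, which section 8.1 itself describes as an assumption made without data on interferon after nucleos(t)ide treatment. With no arm effect on HBsAg loss, false entry disappears and little harm remains.

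The analysis is exploratory. The primary comparison and the sample size are untouched. Severity is minor to moderate.

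**What to change.** In section 8.2(iii), state that treatment group is included in the single-variable models, at minimum for every variable measured after randomisation, and that the arm-adjusted odds ratios are the ones reported and used for selection. State also whether ELISPOT counts are baseline or post-baseline values.

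Do not require the randomisation strata in every model. Gender and HBsAg titre are themselves candidates. The biopsy variables exist in only about 20 patients: at 30% pooled loss that is about 6 events (20×0.30), too few for marker, treatment group, gender and titre together. Those variables precede randomisation, so they do not need the adjustment for this reason.

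The cost is one or two sentences in the protocol, carried into the SAP, with no new data or patients. Where a marker does not differ by arm nothing is lost: detection of a predictor with odds ratio 1.5 is 71% without treatment group and 73% with it.

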9 REGULATORY, ETHICAL AND LEGAL ISSUES

9.1 Treatment

9.1.1 Investigational Medicinal Product Details

Drug Name	Dosage	Description
Pegylated Interferon	180 mcg o.w. s.c. α2a	Standard pharmacy supplies of this licensed medication will be issued on regular prescriptions with no specific trial labelling.

9.1.2 Labelling, storage and dispensing

Labelling, storage and dispensing will be as per routine pharmacy clinical procedures using standard pharmacy supplies. Trial-specific labelling is not required as the IMP does not require any particular manufacturing or packaging processes, it has an MA, is used within its MA, is prescribed by a healthcare professional and is labelled according to The Medicines for Human Use Regulations 1994.

9.1.3 Accountability

There are no requirements for accountability or shipping and destruction records for the trial as the IMP is used within its authorisation and prescribed from routine stock in the NHS. We will monitor, and record on the eCRF, patient adherence to pegylated interferon therapy as described in section 6.1 as a safety endpoint.

9.2 Declaration of Helsinki

The investigator will ensure that this study is conducted in full conformity with the 7th revision of the 1964 Declaration of Helsinki.

9.3 Good Clinical Practice

The study will be conducted in accordance with the guidelines laid down by the International Conference on Harmonisation for Good Clinical Practice (ICH GCP E6 guidelines).

9.4 Independent Ethics Committee Approval

(i) Initial Approval

Prior to the enrolment of subjects, the REC must provide written approval of the conduct of the study at named sites, the protocol and any amendments, the Subject Information Sheet and Consent Form, any other written information that will be provided to the subjects, any advertisements that will be used and details of any subject compensation.

(ii) Approval of Amendments

Proposed amendments to the protocol and aforementioned documents must be submitted to the REC for approval as instructed by the Sponsor. Amendments requiring REC approval may be implemented only after a copy of the REC's approval letter has been obtained.

Amendments that are intended to eliminate an apparent immediate hazard to subjects may be implemented prior to receiving Sponsor or REC approval. However, in this case, approval must be obtained as soon as possible after implementation.

(iii) Annual Progress Reports

The REC will be sent annual progress reports in accordance with national requirements.

(iv) Annual Safety Reports and End of Trial Notification

The REC will be sent annual safety updates in order to facilitate their continuing review of the study (reference. ICH GCP E6 Section 3.1.4) and will also be informed about the end of the trial, within the required timelines.

9.5 Regulatory Authority Approval

The study will be performed in compliance with UK regulatory requirements. Clinical Trial Authorisation from the Medicines and Healthcare Products Regulatory Agency (MHRA) will be obtained prior to the start of the study. In addition, the MHRA will approve amendments prior to their implementation (as instructed by the Sponsor), receive SUSAR reports and annual safety updates, and be notified of the end of the trial.

9.6 R&D Approvals

R&D approval will be obtained from each participating site before any trial procedures commence at that site.

9.7 Insurance and Indemnity

Imperial College London, the Sponsor of the trial has civil liability insurance, which covers this study in all participating centres. Imperial College London also holds negligent harm and non-negligent harm insurance policies which apply to this study.

9.8 Trial Registration

The study will be registered on a trial database (clinicaltrials.gov and/or ISRCTN) in accordance with requirements of the International Committee of Medical Journal Editors (ICMJE) regulations.

9.9 Informed Consent

Informed consent will be obtained from all participants. Patient information sheets and consent forms will be provided in English, Urdu and Mandarin. Translation services provided by the NHS will be used to ensure that patients' questions or concerns are appropriately addressed.

The patient will be informed about the trial by the responsible clinician or a member of the research team and given a copy of the Patient Information Sheet (PIS). Informed patients will be given an adequate amount of time to consider their participation in the trial. If the patient decides to participate in the trial they will be asked to sign the Patient Consent Form which will then be countersigned by the responsible clinician / researcher. The patient will retain one copy of the signed Consent Form. Another copy will be placed in the patient's medical records whilst the original will be retained in the research record for the patient at sites.

NL	JC-B	

The right of the participant to refuse to participate without giving reasons must be respected. All participants are free to withdraw at any time from the protocol treatment without giving reasons and without prejudicing further treatment.

9.10 Contact with General Practitioner

It is the investigator's responsibility to inform the subject's General Practitioner by letter that the subject is taking part in the study provided the subject agrees to this, and information to this effect is included in the Patient Information Sheet and Informed Consent. A copy of the letter should be filed in research record for the patient at sites.

9.11 Subject Confidentiality

The investigator must ensure that the subject's confidentiality is maintained. On the CRF or other documents submitted to the Sponsors, subjects will be identified by a subject ID number only. Documents that are not submitted to the Sponsor (e.g., signed informed consent form) should be kept in a strictly confidential file by the investigator.

The investigator shall permit direct access to subjects' records and source document for the purposes of monitoring, auditing, or inspection by the Sponsor, authorised representatives of the Sponsor, Regulatory Authorities and RECs.

9.12 Data Protection

All personnel involved in the study will observe or work within the confines of the local data protection guidelines.

9.13 End of Trial

The end of the trial will be last patient last visit.

9.14 Study Documentation and Data Storage

The investigator will retain essential documents until notified by the Sponsor, and for at least ten years after study completion. Patient files and other source data (including copies of protocols, CRFs, original reports of test results, IMP dispensing logs, correspondence, records of informed consent, and other documents pertaining to the conduct of the study) will be retained. Documents will be stored in such a way that they can be accessed/data retrieved at a later date.

No study document will be destroyed without prior written agreement between the Sponsor and the investigator. Should the investigator wish to assign the study records to another party or move them to another location, written agreement must be obtained from the Sponsor.

10 DATA MANAGEMENT

10.1 Source Data

Source documents include original documents related to the trial, to medical treatment and to the history of the participant, and adequate source documentation must be maintained to allow reliable verification and validation of the trial data. What constitutes the source data for this trial will be outlined in the study Monitoring Plan.

10.2 Language

CRFs will be in English. Generic names for concomitant medications should be recorded in the CRF wherever possible. All written material to be used by subjects must use vocabulary that is clearly understood, and be in the language appropriate for the study site. Patient information sheets and consent forms will be provided in English, Urdu and Mandarin.

10.3 Database

Electronic CRF: the principal means of data collection from participant visits will be Electronic Data Capture (EDC) via the internet using the InForm database. Data is entered into the EDC system via site personnel. All source data recorded in the CRF will be signed by the Investigator or his/her appropriate designee. All changes made following the electronic signing will have an electronic audit trail with a signature and date. Specific instructions and further details will be outlined in the CRF manual.

